### **Methodology**

The proposed study will consist of a 13 week double-blind cross-over study trial of milk thistle in 25 people (ages 10-65). The study will be divided into an initial 6 week phase, a 1 week wash-out phase, and a second 6 week phase, with one of the 6 week phases consisting of active treatment with milk thistle, and one of the 6 week phases consisting of inactive placebo treatment. Participants will be randomized to receive either milk thistle or placebo during the first 6 week phase on a 1:1 basis. This blinding will be maintained by the IDS pharmacy at the University of Chicago.

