### **Study Design**

The study is a 13-week, double-blind, placebo-controlled, pilot study of the safety and efficacy of milk thistle for children and adults with trichotillomania. All eligible study subjects will go through a 6-week treatment phase during which they will begin milk thistle at 300mg twice a day. Subjects will be given a matching placebo during the 6-week placebo phase. Subjects will be seen for scheduled study visits every two weeks during the 6-week blinded phases, with an additional visit one week after the end of the first 6 week phase, corresponding with the end of the 1 week wash-out period. Subjects will be randomized to either receive either the active or placebo condition during the first 6-week phase, and the remaining condition during the second 6-week phase. All efficacy and safety assessments will be performed at each visit. Subjects who are not compliant with their use of study medication (i.e. failing to take medication for three or more consecutive days) will be discontinued from the study. Patients who experience a clinically significant adverse event will also be discontinued from the study.

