### **Screening Assessments**

1. Demographic data and clinical characteristics will be recorded for each subject (baseline visit).
2. Formal screening psychiatric interview for each subject including the Mini International Neuropsychiatric Inventory (10) (baseline visit).
3. Symptom severity at baseline and follow-up visits will be examined using reliable and valid scales:
  - a. *Massachusetts General Hospital Hairpulling Scale* (MGH-HPS) (11) (each visit)

- b. *Trichotillomania Scale for Children, Child Version (TSC-C)* (12) (each visit) (only for children under the age of 18 who are participating in the study)
- c. *Trichotillomania Scale for Children, Parent Version (TSC-P)* (12) (each visit) (only for parents of children under the age of 18 who are participating in the study)
- d. *NIMH Trichotillomania Symptom Severity Scale (TSS)* (13) (each visit)
- e. *Clinical Global Impression severity and improvement scales* (14) (each visit)
- f. *Sheehan Disability Scale* (15) (baseline and final visit)
- g. *Hamilton Anxiety Rating Scale (HAM-A)* (16) (each visit)
- h. *Hamilton Depression Rating Scale (HAM-D)* (17) (each visit)
- i. *Lie Acceptability Scale (Baseline)*
- j. *The Narcissistic Personality Inventory 16 (Baseline)*
- k. *The Social Desirability Scale (Baseline)*

*Massachusetts General Hospital Hair Pulling Scale (MGH-HPS)* (11). The MGH-HPS is a 7-item, self-report scale that rates urges to pull hair, actual amount of pulling, perceived control over behavior, and distress associated with hair pulling over the past seven days. Analysis of the MGH-HPS has demonstrated two separate factors with acceptable reliability for both: “severity” and “resistance and control.”

*Trichotillomania Scale for Children (TSC-C & TSC-P) (Parent and Child Versions)* (12). The TSC is a validated measure of trichotillomania symptom severity in children. These scales assess parent and child reports of frequency of pulling behavior as well as other facets of severity and impairment. (Tolin et al., 2008)

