*NIMH Trichotillomania Severity Scale (NIMH-TSS)* (13). The NIMH scale is a 5-item, clinician-administered scale that rates hair pulling symptoms during the past week. The items assess pulling frequency (both on the previous day and during the past week), urge intensity, urge resistance, subjective distress, and interference with daily activities. Four items are rated from 0 (none) to 5 (most severe) and the final item is rated from 0 to 4. A total score is calculated by summing all the item scores. The NIMH-TSS has demonstrated sensitivity to changes in symptom severity.

*Clinical Global Impression- Severity and Improvement (CGI)* (14). The CGI consists of a reliable and valid 7-item Likert scale used to assess severity and improvement in clinical symptoms. The CGI severity scale was used at each visit and ranges from 1 = “not ill at all” to 7 = “among the most extremely ill.” The CGI Improvement scale was used at each follow-up visit and ranges from 1 = “very much improved” to 7 = “very much worse.”

*Sheehan Disability Scale (SDS)* (15). The SDS is a three-item, reliable and valid self-report scale that assesses functioning in three areas of life: work, social or leisure activities, and home and family life. Scores on the SDS range from 0 to 30.

*Hamilton Anxiety Rating Scale (HAM-A)* (16). The HAM-A is a reliable and valid, clinician-administered, 14-item scale that provides an overall measure of global anxiety.

*Hamilton Depression Rating Scale (HAM-D) (17)*. The HAM-D is a valid and reliable, 17-item, clinician-administered rating scale assessing severity of depressive symptoms.

*Cambridge-Chicago Trait Scale (Cambridge CHI-T Scale) (18)*. The CHI-T scale is a 16-item self-report scale that measures compulsivity.

*Lie Acceptability Scale (Goosie, 2014)*: An 11-item self-report questionnaire which assesses an individual's perception of the acceptability of lying across several dimensions.

*The Narcissistic Personality Inventory 16 (Raskin & Terry, 1988)*: The NPI-16 is a short measure of subclinical narcissism that has shown meaningful face, internal, discriminant, and predictive validity. It can serve as an alternative measure of narcissism when situations do not allow the use of longer inventories.

*The Social Desirability Scale (Crowne & Marlowe, 1960)*: A 33-item self-report questionnaire which assesses the degree to which individuals report the outcome that is most socially desirable using true/false questions.

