### Data Analysis

Demographic and baseline visit characteristics for milk thistle and placebo groups will be compared using chi-square and analysis of variance to determine if group differences existed at randomization. Given the crossover design, both the placebo and the active milk thistle groups will contain an N of 25. Primary and secondary measures will be examined using repeated-measures ANOVA modeling analyses (PROC MIXED, SAS/STAT Software for Windows, Version 8.2, SAS Institute Inc., Cary, NC, USA). The baseline value of the measure being analyzed will be used as a covariate. A time trend (linear) will be included in all models. The difference in the overall level of posttreatment values, the main effect for treatment, will be the test of primary interest. Analyses will be performed on all available data as well as for the completers. All available post-randomization data will be first analyzed and a secondary, supportive analysis of completers will be performed. All comparison tests will be two-tailed and an alpha level of .05 will be used to determine statistical significance given the exploratory nature of the study.

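### Does the plan need a written rule for the end-of-wash-out (week-7) score in the treatment contrast?

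*Combined protocol and SAP*

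**What the plan says.** The Data Analysis section fits a repeated-measures model with the baseline score as covariate. On time it says "A time trend (linear) will be included in all models", and on the test itself "The difference in the overall level of posttreatment values, the main effect for treatment, will be the test of primary interest". The first analysis takes all data available after randomization, and an analysis of completers supports it. For significance, "All comparison tests will be two-tailed and an alpha level of .05 will be used", which the section justifies by the exploratory nature of the study.

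The Methodology section divides the 13 weeks into "an initial 6 week phase, a 1 week wash-out phase, and a second 6 week phase". The Study Design section sets visits every two weeks within each blinded phase and adds "an additional visit one week after the end of the first 6 week phase, corresponding with the end of the 1 week wash-out period". It also says "All efficacy and safety assessments will be performed at each visit". The Screening Assessments list agrees for the primary scale: "NIMH Trichotillomania Symptom Severity Scale (TSS)* (13) (each visit)". That scale is described as a "clinician-administered scale that rates hair pulling symptoms during the past week".

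The visits are therefore weeks 2, 4 and 6, then week 7, then weeks 9, 11 and 13 (7+2, 7+4, 7+6). A primary-scale score will exist at week 7, and its recall period is exactly the wash-out week. No section says how it enters the treatment comparison or whether it serves as a baseline for the second phase.

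**The concern.** Week 7 falls after randomization, so a literal reading of the all-data rule brings it into the model. The model compares only milk thistle and placebo, and week 7 belongs to neither. An analyst could leave it out, code it as off drug (the same as placebo), or carry the label of the phase before or after it. The last two look wrong for a week without assigned treatment, but nothing in the text forbids them.

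At stake are the size of the primary estimate and its power. A score filed under a label it does not deserve pulls the estimate towards no effect. If the coding were picked after seeing the results, the false-positive rate would also rise above 5%.

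**Working it through.** **What the text already settles.** The contrast is an overall level, the model has a linear time trend, and all data after randomization are used. That points to an average over the scheduled on-treatment visits, which Study Design fixes as weeks 2, 4, 6, 9, 11 and 13. Only week 7 is open.

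**Inputs.** From the documents: 25 participants, 1:1 allocation to order (taken as 13 active first, 12 active second), the seven visit weeks, the linear trend, two-sided 0.05. The plan gives no power, effect size, standard deviation, correlation or covariance structure, so there is no figure of its own to reproduce. Assumptions: outcome SD 1; both phases complete; constant on-drug effect of 1; a share r of that effect left at week 7; baseline covariate omitted; no carryover from week 9 except where stated. Two covariance structures were used: equal correlation between visits (0.3 to 0.7), and a person component of 0.3 plus serial correlation 0.8 per week, V = 0.3 + 0.7 × 0.8^(weeks apart).

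**Method.** Generalised least squares with intercept, week and treatment. The coefficient is (ΣX′V⁻¹X)⁻¹ΣX′V⁻¹μ, where μ is the true mean profile.

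**Hand check under equal correlation 0.5.** Using within-patient sums of squares of the treatment indicator, and ignoring the slight effect of the time trend:

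- Week 7 excluded: 6 visits, 3 on drug, 3 − 9/6 = 1.5 per patient. SE = √(0.5/(25 × 1.5)) = 0.1155.
- Week 7 coded off drug: 7 visits, 3 on drug, 3 − 9/7 = 1.714. SE = √(0.5/(25 × 1.714)) = 0.1080.
- Ratio: 0.1155/0.1080 = 1.07, so exclusion costs about 7% in standard error.
- Off-drug coding with r = 1: active-first patients contribute 3 − 3 × 4/7 = 1.286 and active-second patients 1.714. Share recovered = (13 × 1.286 + 12 × 1.714)/(25 × 1.714) = 0.87.

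The full model gives the same values.

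**Share of the true effect recovered:**

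| Week-7 handling | Equal correlation 0.3-0.7, r = 0 | r = 1 | Serial structure, r = 0 | r = 1 |
|---|---|---|---|---|
| Excluded | 1.00 | 1.00 | 1.00 | 1.00 |
| Off drug | 1.00 | 0.87 | 1.00 | 0.46 |
| First-phase label | 0.87 | 1.00 | 0.63 | 1.00 |
| Second-phase label | 0.88 | 0.74-0.75 | 0.60 | 0.17 |

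Under the serial structure the standard error is 0.150 with exclusion and 0.112 with off-drug coding: 0.150/0.112 = 1.34, or 34% larger.

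**Power under equal correlation**, with exclusion set at 80% as a reference (noncentral t, 23 df): off-drug coding gives 85% at r = 0, 80% at r = 0.5 and 74% at r = 1.

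**Carryover beyond week 7.** Take assumed residuals of 0.7, 0.34 and 0.17 at weeks 7, 9 and 11. With week 7 excluded, active-first patients contribute 3 − 3 × 3.51/6 = 1.245, so the share is (13 × 1.245 + 12 × 1.5)/37.5 = 0.91. The full model gives 0.91 under equal correlation and 0.88 under the serial structure. Exclusion therefore does not free the estimate from incomplete wash-out.

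**False positives.** In a null simulation (100,000 data sets per correlation, equal correlation) each fixed coding rejected in 4.9-5.0%. Taking the better of exclusion and off-drug coding gave 6.6-6.7%; the best of all four gave 9.3-9.4%.

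**The case for a change.** The strongest case for adding text is that this is the primary test, the all-data wording leans towards including week 7 without saying how, and a sentence costs nothing. Equal correlation is also not the worst case. With serial correlation and an effect that builds up over each phase, readings that use week 7 as an outcome range from 0.11 to 1.00 of the full effect. It can be added that the word posttreatment might mean the end of each phase only.

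Some of this stands. The gap exists, and the choice can matter under strong serial correlation with a large residual effect. But the lowest values come from giving week 7 the second-phase label, which means treating a week before that phase began as if it were on its treatment. A crossover analyst has no reason to do that. An end-of-phase reading sits badly with an overall level, a linear trend and the use of all data.

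Nor is the one-sentence remedy as clean as it sounds. Making week 7 descriptive would contradict the all-data rule unless that rule were amended too. It would leave open whether week 7 is the second-phase baseline. It would also give up precision, 7% to 34% in standard error, that off-drug coding keeps when wash-out is complete.

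**Conclusion.** No change follows. The plan leaves one visit's handling unstated. The two natural ways of handling it are both unbiased if the drug effect has gone by week 7, and both keep the 5% error rate when fixed in advance. Choosing between them trades precision against sensitivity to a residual effect. The documents give neither the covariance structure nor the residual effect needed to say which is better. The exposure from a choice made after seeing the data is 6.6-6.7% against 5%, and nothing in the plan suggests such a choice. For a 25-person pilot that calls its testing exploratory, this is a detail that analysts fill sensibly.

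The sizes rest on assumed correlations, a constant effect, complete data and no baseline covariate, so they show a range and are not predictions. The absence of period, sequence and carryover terms is a separate matter, as is the contrast for measures listed only at baseline and the end of the study.

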Aim 2: Because lack of cognitive control may underlie a range of body-focused repetitive behaviors, and improvement in related systems may be secondary to greater control, we will examine levels of cognitive control using cognitive tasks pre- and post-treatment. This study will examine cognitive deficits across a range of prefrontal-dependent domains which have been associated with trichotillomania – response inhibition, working memory, cognitive flexibility and planning ability - as possible predictors of treatment and as possible biomarkers for underlying pathophysiology of hair pulling behavior. We hypothesize that improvement in response inhibition will be greater in participants who receive milk thistle compared with placebo.

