*Cognitive Assessments*: In addition, subjects will undergo cognitive assessments at baseline and study endpoint. Assessments of cognitive control will be comprised of several valid paradigms (Table 1). These tasks are designed to probe dissociable neural circuitry and cognitive processes likely to be implicated in the pathophysiology of body-focused repetitive behaviors. Task order will be chosen arbitrarily and will be applied consistently across subjects, to minimize possible confounding factors of differences in task order across participants.

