### **Efficacy Assessments**

**The primary outcome measure will be the NIMH Trichotillomania Severity Scale (NIMH-TSS)**. The NIMH-TSS is a reliable and valid scale that is frequently used in research to assess symptom severity.

Secondary efficacy measures include

- *The Clinical Global Impression-Improvement and Severity scales (CGI)*
- *Massachusetts General Hospital Hair Pulling Scale (MGH-HPS)*

- *Trichotillomania Scale for Children (TSC-C & TSC-P) (Parent and Child Versions)*
- *Sheehan Disability Scale (SDS)*
- *Hamilton Anxiety Rating Scale (HAM-A)*
- *Hamilton Depression Rating Scale (HAM-D).*
- *Cambridge-Chicago Trait Scale (Cambridge CHI-T Scale)*

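### The plan lets every comparison, not only the named primary, be called statistically significant at an unadjusted two-sided .05 because the study is exploratory

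*Combined protocol and SAP*

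**What the plan says.** The Data Analysis section sets one rule for the whole trial: "All comparison tests will be two-tailed and an alpha level of .05 will be used to determine statistical significance". The reason follows in the same sentence: "an alpha level of .05 will be used to determine statistical significance given the exploratory nature of the study". The documents contain no adjustment, testing order or gatekeeping, and no statement that any result is descriptive only.

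The plan does set some priorities. Efficacy Assessments names the NIMH-TSS as the single primary outcome. Data Analysis identifies one contrast: "The difference in the overall level of posttreatment values, the main effect for treatment, will be the test of primary interest". It analyses all available post-randomization data first and labels the completer analysis secondary and supportive.

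The other outcomes are numerous. The list headed "Secondary efficacy measures include" has seven entries, which yield nine scores: CGI-Improvement, CGI-Severity, MGH-HPS, TSC-C, TSC-P, SDS, HAM-A, HAM-D and CHI-T. For cognition, "Assessments of cognitive control will be comprised of several valid paradigms", and Table 1 lists six tasks besides the training task. Aim 2 attaches one treatment hypothesis to them: "We hypothesize that improvement in response inhibition will be greater in participants who receive milk thistle compared with placebo".

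**The concern.** An exploratory purpose is normally a reason to hold back from significance claims on secondary outcomes. Here it is given as the reason for making them without adjustment. This is a stated rule and not just an omission, because the sentence covers all comparisons and says what the .05 level is for.

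What is at stake is the reading of the trial if the NIMH-TSS shows nothing. With 25 participants and no power calculation in the documents, a null primary is a real possibility. The plan would then permit a difference on any secondary scale or cognitive task to be reported as a significant effect. Specific Aims says the results are meant to inform clinicians about treatment options for children and adults, so the label would carry weight.

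**Working it through.** The plan states a per-test level of .05 and no family-wise error rate, so there is no derived figure to reproduce. The check asks how often at least one test reaches p < .05 if silymarin has no effect on anything and each test has its nominal size.

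**How many tests.**
- *Seven scores.* Screening Assessments lists CGI-S, CGI-I, MGH-HPS, TSC-C, TSC-P, HAM-A and HAM-D at each visit. The two TSC versions apply only to participants under 18.
- *Nine scores.* This adds SDS and CHI-T. Screening Assessments puts SDS at baseline and final visit only and gives CHI-T no visit. Study Design, however, says that all efficacy assessments are done at every visit, so both counts have some support in the text.
- *Fifteen tests.* This adds the six non-training tasks of Table 1, at one score per task. The number of scores per task is not stated. The tasks are scheduled only at baseline and study endpoint, and Data Analysis names only primary and secondary measures in its model.

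**Independent tests, one analysis set.** The chance of at least one false result in either direction is 1 − 0.95^k. A two-sided .05 test puts 0.025 in the direction of benefit, so the chance of at least one false benefit is 1 − 0.975^k.

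| k | Either direction | Benefit only |
|---|---|---|
| 7 | 1 − 0.95^7 = 30.2% | 1 − 0.975^7 = 16% |
| 9 | 1 − 0.95^9 = 37.0% | 1 − 0.975^9 = 20% |
| 15 | 1 − 0.95^15 = 53.7% | 1 − 0.975^15 = 32% |

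With 15 tests the expected number of false positives is 15 × 0.05 = 0.75.

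**Correlated tests, one analysis set, either direction.** The documents give no correlations, so these are assumptions. The figures come from simulating multivariate-normal test statistics (400,000 draws, two-sided .05).

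| Assumed common correlation | 7 scores | 9 scores | 15 tests |
|---|---|---|---|
| 0.2 | – | – | 50% |
| 0.3 | 27% | 33% | 46% |
| 0.5 | 23% | 27% | 36% |

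Allowing the nine clinical scores, the six cognitive tasks and the two groups jointly to have different correlations gives a similar picture for 15 tests. Correlations of 0.5 (clinical), 0.2 (cognitive) and 0 (between) give 46%; correlations of 0.7, 0.4 and 0.2 give 38%.

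**Both analysis sets.** If the completer results are also open to significance claims, with an assumed correlation of 0.9 between sets, the figures for 15 outcomes are 67%, 58% and 47% at common correlations of 0, 0.3 and 0.5.

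**Primary.** The NIMH-TSS treatment effect is one pre-named contrast. Its error rate does not depend on how many other outcomes are tested.

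**The case against.** The strongest defence is that this is a disclosed choice in a 25-person pilot. One primary outcome and one contrast are named, the other measures are labelled secondary, and the completer analysis is called supportive. Aim 2 states only one directional cognitive hypothesis, and in Table 1 only the Stop-Signal task targets response inhibition. A reader who saw a null NIMH-TSS and one positive secondary scale could judge it accordingly.

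That ordering is real and it protects the primary analysis. It does not limit the significance rule, which covers every comparison regardless of rank.

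A reader might also infer that a false significant finding is about as likely as not. The documents do not support that as a general statement. It needs 13 to 15 independent tests (49% to 54%) in one analysis set, and several of those are doubtful. The cognitive tasks are not named in the model. They and the SDS, as listed, are taken only at baseline and the end, when crossover completers have had both treatments. Independence is also implausible, since the CGI, MGH-HPS and TSC scores all largely track hair-pulling severity. Counting the completer repeat or several scores per task would push the figure up again, but the documents do not state the number of scores.

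Nor do the either-direction figures measure false claims of benefit. They include false findings that silymarin is worse.

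**Conclusion.** The point holds as a cheap improvement. The plan applies an unadjusted .05 significance rule to all outcomes and uses the exploratory label to justify it. If silymarin does nothing, the chance of at least one false significant result in one analysis set runs from about 30% or less (seven scores) to 54% (15 independent tests). For a false benefit alone, the independent-test figures are 16% and 32%. Even 16% is more than six times the 2.5% of a single test (0.16 / 0.025 = 6.4).

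These sizes rest on the assumed count of tests, the assumed correlations and one score per cognitive task. The documents settle none of these.

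A reader might take this as a flaw in the primary analysis or as a call for a Bonferroni-type correction. Neither follows: the NIMH-TSS test keeps its .05 level, and the problem is solved by limiting what is claimed.

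**What to change.** Replace the sentence on the alpha level in Data Analysis with:

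> Two-sided alpha .05 applies to the treatment effect on the NIMH-TSS in the all-available-data analysis only. All other measures, including the cognitive tasks, and the completer analysis are reported as estimates with 95% confidence intervals and nominal p-values and will not be called statistically significant.

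For Aim 2, name the stop-signal response-inhibition measure as the main exploratory estimate, with no significance claim, and describe the other tasks as descriptive. This does not resolve the baseline-and-endpoint timing of the cognitive tasks, which is a separate matter.

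The cost is a small edit to the analysis text. Every measure is still analysed and reported, and the power of the primary test does not change. The one downside is that secondary and cognitive findings cannot be presented as significant.
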